11.2.7 Visit 6 at 15 months

The following assessments must be performed:

- physical and neurological examination including vital signs (SBP and DBP, heart rate),
- electrophysiology testing of sensory and motor responses of ulnar and radial nerves on the non-dominant side, including CMAP, SNAP, NCV, and DML parameters.
- clinical scores and functional tests will be assessed:
 - CMTNS score
 - ONLS score
 - 9-Hole Peg Test in non-dominant limb
 - quantified muscular testing (hand grip and foot dorsiflexion on both sides)
 - 10 m Walking test
- quality of life measured by:
 - EuroQol 5-Dimensional Health-related Quality of Life scale (EQ-5D);

- VAS on self-assessment of the individualized main impairment in daily activities defined at baseline with the patient;
- review of concomitant treatments,
- review of Adverse Events,
- blood sample for biomarkers,
- blood samples for PK (one before dosing, and one 90 minutes after drug intake)
 - Attention: PK samples are not applicable in the dose 2 arm if the end of study visit is performed due to discontinuation of the dose 2 arm.
- blood sample for safety,
- 12-lead ECG (sent for centralized reading by a cardiologist);
- skin biopsy (optional /ancillary study),
- leg MRI (optional /ancillary study),
- review of compliance to study drug and drug accountability

11.3 Subject withdrawal

In accordance with the Declaration of Helsinki, patients will be free to withdraw from the study at any time if they wish to do so, for any reason specified or unspecified.

Before the final scheduled study visit, the investigator has the responsibility and the right to end patient participation in the study. For non-emergency situations, listed below, the investigator is required to contact the sponsor or their representative before implementing his/her decision.

11.4 Criteria for subject withdrawal from the trial

Patient may be withdrawn from the study in the following circumstances:

- voluntary withdrawal of patient consent, loss of follow-up or patient inability to remain under medical observation,
- non-compliance or major deviation from the protocol,
- deterioration of patient's condition which no longer enables him/her to comply with the protocol,
- Appearance of a Serious Adverse Event (SAE) or any other situation where, in the opinion of the investigator, continuation in the study would not be in the best interests of the subject.

Should any of the subjects be withdrawn from the study then the reason(s) for withdrawal must be recorded in the e-CRF and in the patient's medical records.

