9.3.2 Forbidden concomitant treatments

The following concomitant treatments are forbidden within 30 days before randomization and during the whole study:

- High doses of Ascorbic acid (≥ 1 g/day)
- Levothyroxin are forbidden.
- Baclofen, naltrexone, and sorbitol in their current pharmaceutical forms at full dose are forbidden.

The use of opiates, such as morphine, fentanyl, oxycodone, buprenorphine, nalbuphine, tramadol, and methadone potentially neurotoxic drugs should also be avoided. A list of non-recommended treatments is provided in Appendix 1.

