11.5 Follow-up for withdrawn patients

When a subject is prematurely withdrawn from the study, before *V6 at 15 months*, the investigator must perform a complete "end of study visit" (as soon as possible) after patient withdrawal.

The Investigator must make every effort to contact patients lost to follow-up. Attempts to contact such patients must be documented in the patient's records (e.g., times and dates of attempted telephone contact, receipt for sending a registered letter). Particularly, effort must be done to obtain data on patient's health status (death: yes/no) and to determine the reason why he/she failed to attend the visit. If death occurs, a death certificate will be collected by the investigator.

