14. STATISTICAL CONSIDERATIONS

14.1 Analysis sets

The **Full Analysis Set (FAS)** will be constituted by all the randomized patients.

The **Per-Protocol (PP)** population will include all the patients of the FAS without major protocol violation during the course of the study.

All the efficacy analyses will be conducted on the FAS population and reproduced on the PP population for sensitivity purposes. The safety analyses will be conducted on the FAS, given that all randomized patients will receive at least one dose of treatment.

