14.5 Missing data

Few missing data were observed in past trials in this pathology. Due to likely expected loss of efficacy after treatment discontinuation, and a possible deterioration compared with baseline values, last or baseline observation carried forward may not be appropriate. Missing values will be imputed using a linear model estimated on the Placebo group. The potential impact of missing data on the study's conclusions will be evaluated. Descriptive data analyses will allow assessing the pattern of missing data, including reasons for drop-outs in each treatment group. In addition, sensitivity analyses will be conducted by using other missing data approaches (further details in the SAP).

For any patient experiencing early trial interruption, an early interruption visit is planned. It will be checked if this visit took place within a given time frame where the next regular visit would have been planned. In case the early interruption visit occurs within this time frame, data of the early interruption visit will be shifted to the next regular visit for all analyses. In case the early interruption visit does not occur within this time frame, the data of the early interruption visit will not be included in any of the inferential analyses.

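### Sections 11.4 and 11.5 do not separate stopping study drug or deviating from the protocol from leaving the study, so 12- and 15-month ONLS that could often be measured may be imputed instead

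*Combined protocol and SAP*

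**What the plan says.** Section 11.4 opens with "Patient may be withdrawn from the study in the following circumstances" and lists, among others, "non-compliance or major deviation from the protocol" and deterioration that leaves the patient unable to follow the protocol. What ends is participation in the study, not only study drug. Section 11.3 asks the investigator to contact the sponsor first in non-emergencies.

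Section 11.5 requires one complete end-of-study visit, to be held "as soon as possible) after patient withdrawal". It describes no later scheduled visit. For patients lost to follow-up, the particular effort asked for is vital status and the reason for non-attendance, not ONLS.

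Section 14.1 says that the FAS "will be constituted by all the randomized patients". The primary analysis (Section 14.2) uses the mean of ONLS at 12 and 15 months, adjusted for baseline.

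Section 14.5 rejects carry-forward methods, giving as its reason: "Due to likely expected loss of efficacy after treatment discontinuation, and a possible deterioration compared with baseline values". Missing values come instead from a linear model fitted to the placebo arm. If the early visit falls within a time frame that is not defined, "data of the early interruption visit will be shifted to the next regular visit for all analyses". If it falls outside, its data are left out of every inferential analysis. Sensitivity analyses by other methods are promised but not described.

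**The concern.** The analysis set and the follow-up rules pull in opposite directions. An analysis of everyone randomised needs a 12- and a 15-month ONLS from each patient, whether or not the patient kept to the protocol or stayed on drug. The follow-up rules allow those measurements to stop for exactly the patients who did not, and the missing-data section then models a value that could often have been observed.

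This affects Dose 1 versus Placebo, the only comparison that continues as planned after the Dose 2 arm was closed. The Dose 2 closure is a separate and larger source of missing data and is not counted here. At stake are a diluted treatment difference and a primary result that leans on an imputation model more than it needs to.

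**Working it through.** **1. How a value is lost.** Follow a patient withdrawn under Section 11.4. The early visit is complete, and the 15-month visit list (Section 11.2.7) includes ONLS, so one score is normally obtained. It counts only if it falls in the time frame of Section 14.5. Withdrawal after month 12 keeps an observed 12-month value. Otherwise both components of the primary endpoint are imputed.

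How often that happens depends on the undefined time frame. Assume that withdrawals are spread evenly over Days 0–450 and that the early visit is immediate. If the time frame equals the ±10-day visit window, withdrawals before Day 350 have neither value: 350/450 = 78%. If every early visit after the Day 270 visit counted as month 12, the share is 270/450 = 60%.

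**2. The plan's own sample size.** Inputs from Section 14.3: SD about 1, R = 0.75, two post-baseline measures, difference 0.3, two-sided 2.5%, power 90%.

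- Adjusted variance under compound symmetry: SD² × [(1 + R)/2 − R²] = 0.875 − 0.5625 = 0.3125, so the adjusted SD is 0.559.
- n = 2 × (2.241 + 1.282)² × 0.3125 / 0.3² = 86.2, so 87 per group. A t-based version gives 88. The stated 89 is reproduced to within two patients.
- 89 / 0.9 = 98.9, so 99, rounded in the plan to 100.

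**3. Effect of imputing placebo-like values.** Let w be the share of each arm withdrawn with both values imputed. The documents do not give w, so 0–30% is an assumed range, equal in both arms. The expected difference is 0.3 × (1 − w). At 100 per group the standard error is 0.559 × √(2/100) = 0.07906, and power is Φ(difference / 0.07906 − 2.241). For w = 10%: 0.27 / 0.07906 − 2.241 = 1.174, giving 88.0%.

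The last two columns come from 4,000 simulated trials per scenario, with a placebo model on baseline ONLS and withdrawals chosen at random.

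| w | Expected difference | Power by formula, full residual variance | Simulated, random residual added | Simulated, deterministic imputation |
|---|---|---|---|---|
| 0 | 0.300 | 94.0% | 94% | 94% |
| 5% | 0.285 | 91.4% | 91% | 93% |
| 10% | 0.270 | 88.0% | 87% | 91% |
| 20% | 0.240 | 78.7% | 79% | 87% |
| 30% | 0.210 | 66.1% | 63% | 81% |

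Simulated type I error stayed between about 2.1% and 2.8% against the nominal 2.5%.

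The plan's 10% inflation treats drop-outs as lost sample: 90 completers with the full 0.3 give 91.3% power. Keeping them in the analysis with placebo-like values is a different situation. With full residual variance, 90% power at 0.27 needs 107 analysed per group.

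**4. What continued collection would recover, at w = 10%.**

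- Full effect persists after withdrawal: the difference stays at 0.30 and power at 94.0%.
- Half persists: 0.30 × (1 − 0.10 × 0.5) = 0.285, power 91.4%.
- None persists: 0.27 and 88.0%. Power is not raised, and is slightly below the 91% under deterministic imputation. The gain is then a measured value in place of a modelling assumption.

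**The case against.** The case against has real substance.

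- Withdrawal is permitted, not required, and the sponsor is contacted first in non-emergencies. The per-protocol set is defined by removing major violators from the FAS, which implies that violators can stay in the study and contribute data. So the plan does not mandate the loss. This stands.
- A reader might infer that taking a forbidden treatment ends participation. The documents do not say so. Section 9.3.2 states "The following concomitant treatments are forbidden within 30 days before randomization and during the whole study" but attaches no consequence, and such use is not on the Section 11.4 list. It would matter only if classed as non-compliance or a major deviation, which nothing in the text does.
- Imputation is not universal, because of the shift rule and retained 12-month values. This stands, although step 1 suggests that those rules rescue a minority of withdrawals under the assumptions there.
- The covariates of the imputation model are not given. ONLS is also measured at month 6, and a model using each patient's own earlier scores would carry forward some observed worsening. This stands; the simulation used baseline only.
- The 10% drop-out allowance also covers withdrawn consent and loss to follow-up, which no amendment recovers. Patients who can no longer comply may not attend. The 10% row is therefore an illustration, not an estimate.
- Version 1.4 is dated 5 December 2017. Recruitment was planned to end in Q4 2016, with last patient out in Q1 2018 (Q3 2018 in Germany). On those dates most patients are at or past Day 360, so little can still be recovered.
- Preferring observed off-drug values is partly a choice of estimand. But the plan has already made that choice by analysing everyone randomised and by aiming its imputation at loss of efficacy after discontinuation.

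**Conclusion.** The point holds as a cheap improvement. The documents do not separate stopping drug or deviating from leaving the study, and the resulting gap in a primary outcome is filled from a placebo-arm model.

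The main expected effect is dilution and lost information. At an assumed 10% withdrawn in each arm, the difference falls from 0.30 to 0.27 and power from 94% to about 88–91%. This rests on equal, random withdrawal in both arms, both values missing, and a baseline-only model. The share withdrawn for these reasons is unknown.

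A reader might infer that the rules bias the trial in the drug's favour or inflate false positives. Nothing in the documents supports that. If worsening patients were lost and predicted too favourably only on Placebo, the placebo mean would look better and the apparent benefit would shrink, since a higher ONLS is worse. If this happened only on Dose 1, the benefit would be flattered. Equal errors at equal withdrawal rates would cancel. The plan gives no figures by arm, and withdrawal that depends on outcome or differs between arms was not simulated.

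**What to change.** Amend Sections 11.4 and 11.5 so that stopping study drug, non-compliance, a major deviation or deterioration does not by itself end data collection. Unless consent is withdrawn, invite the patient to the remaining scheduled visits, at least for ONLS at Day 360 and Day 450. Include those observed values in the FAS primary analysis if taken before any entry into the extension study, and limit Section 14.5 imputation to values still missing. Define the early-visit time frame in Section 14.5. Apply the change to patients still in follow-up.

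Section 12.6 requires withdrawal on pregnancy. The amendment should state whether that also ends data collection, so that the sections agree. Decisions about study drug and clinical care are unchanged.

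The cost is a short amendment and up to two already-planned visits for a small group of patients. Some values will be measured off drug, which an all-randomised analysis already accepts.

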11.5 Follow-up for withdrawn patients

When a subject is prematurely withdrawn from the study, before *V6 at 15 months*, the investigator must perform a complete "end of study visit" (as soon as possible) after patient withdrawal.

The Investigator must make every effort to contact patients lost to follow-up. Attempts to contact such patients must be documented in the patient's records (e.g., times and dates of attempted telephone contact, receipt for sending a registered letter). Particularly, effort must be done to obtain data on patient's health status (death: yes/no) and to determine the reason why he/she failed to attend the visit. If death occurs, a death certificate will be collected by the investigator.

11.6 Study discontinuation

11.6.1 Criteria for terminating the trial

Pharnext reserves the right to terminate the study but intends only to exercise this right for valid scientific or administrative reasons and reasons related to protection of patients. In all cases the Ethics Committee (IRB/IEC) and Health Authorities should be informed. Possible reasons for the study termination can include, but are not limited to;

- the discovery of an unexpected, significant or unacceptable risk to patients enrolled in the study
- a decision on the part of Pharnext to suspend or discontinue the development of the investigational product
- request by the relevant regulatory agency
- decision of the DSMB

If the study is prematurely discontinued then enrolled patients should be called for an “end of study visit”

11.6.2 Criteria for terminating a site

Pharnext reserves the right to terminate the study at a given site at any time after the study initiation should any of the followings occur:

- ICH GCP regulations have not been observed,
- the protocol has been violated without justification,
- the data generated are of poor quality,
- changes in personnel or facilities adversely affect performance of the study (e.g. low rate of inclusion).

11.7 Follow up extension study

At the end of the study, patients having completed the study will be eligible to receive PXT3003 in a **9-month follow-up extension trial**, since upon the investigator's judgement they are likely to benefit from use of the medication and if they are willing to prolong their participation in the trial.

The follow-up study will be defined by a **separate protocol**, a new information about this second study will be delivered to the patient, and he will have to provide a new written informed consent.

All the patients randomized to Dose1 or Dose 2 of PXT3003 in this primary study will continue the extension study at the same dose, while patients receiving placebo will be assigned to one of the two doses according to 1:1 randomization. Thus all patients will receive active study drug for 9 extra months in double blind.

First, this extension study will stimulate the recruitment in the primary 15-month study by encouraging patients to be enrolled if they can benefit from active treatment.

Second, it will provide additional long-term data (up to 2 years) on safety and efficacy in double blind design with delayed start for placebo group switched to active dosages of PXT3003 that may provide some evidence of disease modifying effect.

From V1.4: adapted section as follows

Patients who completed this 15-month study or who were prematurely discontinued from the PXT3003 dose 2 administration will be offered to enter the open-label extension study CLN-PXT3003-03.

Patients previously assigned to dose 2 PXT3003 will receive the equivalent of dose 2 (i.e. 5 mL per administration), by use of its equivalent dose, i.e. twice the dose 1 PXT3003 (2x5 mL, i.e. 10 mL per administration) in the study CLN-PXT3003-03.

Patients previously assigned to dose 1 PXT3003 or placebo and who have completed the pivotal phase III study will receive dose 1 PXT3003 (5 mL) in the study CLN-PXT3003-03.

Hence the protocol of extension study has been amended to assign all placebo patients to dose 1 IMP only, whereas patients previously assigned to dose 1 IMP will continue to do so. As a consequence of the difference of IMP volume (i.e. 5 mL and 10 mL) to be administered the study has become an open-label study that no longer randomizes patients to study treatment.

12. SAFETY ASSESSMENTS AND REPORTING

12.1 Adverse Events

12.1.1 Definitions

12.1.1.1 Adverse Events (AEs)

The term **Adverse Event** covers any sign, symptom, syndrome, or illness which appears or worsens in a patient during the observation period of the clinical study and which may impact upon the patient's well-being.

The AE reporting period therefore starts with the patient signing the Informed Consent Form and ends one month after the last administration of study drug. Events occurring during the drug-free and pre- and post-treatment periods should also be designated as adverse events.

The term also covers laboratory findings or results of other diagnostic procedures which are considered to be clinically relevant (e.g. that require unscheduled diagnostic procedures or/and treatment measures or result in withdrawal from the study).

An adverse event may be:

- a new illness,
- the worsening of a sign or symptom of the condition under treatment or of a concomitant illness,
- an effect of the study medication,
- a combination of two or more of these factors.

No causal relationship with the study medication or with the clinical study itself is implied by the use of the term "Adverse Event."

Vital signs and ECG abnormalities, abnormal laboratory values, showing significant shifts from baseline that the investigator considers to be clinically significant, have to be reported as Adverse Event (If there are symptomatic and/or requiring either corrective treatment or consultation, and/or leading to IMP discontinuation or modification of dosing, or fulfilling a seriousness criteria).

Surgical procedures themselves are not adverse events; they are therapeutic measures for conditions that require surgery. The condition, for which surgery is required, may be an adverse event, if it occurs or is detected during the study period. Planned surgical measures permitted by the clinical study protocol and the condition(s) leading to these measures are not adverse events, if the condition(s) was (were) known before the patient signs the informed consent. In the latter case, the condition should be reported as medical history.

12.1.1.2 Treatment Emergent Adverse Events (TEAEs)

A treatment-emergent adverse event is defined as any event not present prior to the initiation of the study treatment, or any event already present which worsens either in intensity or frequency following the exposure to the study treatment.

12.1.1.3 Serious Adverse Events (SAEs)

A serious adverse event (SAE) is any untoward medical occurrence that at any dose:

- results in death;
- is life-threatening¹,
- requires patient's hospitalization or prolongation of existing hospitalization²,
- results in persistent or significant disability/incapacity³,
- is a congenital anomaly/birth defect;
- is medically important⁴.

1 "Life-threatening" means that the patient is at immediate risk of death at the time of the serious adverse event; it does not refer to a serious adverse event that hypothetically might have caused death if it was more severe.

2 'Hospitalization' is defined as inpatient care that covers more than one calendar day.

3 "Persistent or significant disability or incapacity" means that there is a substantial disruption of a person's ability to carry out normal life functions.

4 Medical and scientific judgment should be exercised in deciding whether adverse events may be considered serious because they jeopardize the patient, or may require intervention to prevent one of the other outcomes listed in the definition above. The list of critical terms (1998 adaptation of WHO Adverse Reaction Terminology Critical Terms List) should be used as guidance for adverse events that may be considered serious because they are medically important.

Cases involving cancer as an Adverse Event should be reported as "serious" using the criterion "medically important" if no other serious criterion is met.

12.1.1.4 SAE waived from expedited regulatory reporting to regulatory authorities

For the purpose of the study the following events will not be designated as a serious adverse event (SAE):

- hospital admission as a part of the normal planned treatment or monitoring of the studied indication and not associated with any deterioration in condition,
- hospitalization or prolongation of hospitalization planned before inclusion in the study,
- admission for diagnostic evaluation of an AE,
- overnight hospitalization due to social or travel reasons.

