Secondary efficacy endpoints	
 - Responders Rate to PXT3003 therapy defined as a patients improving on ONLS at end of treatment; - The effect of the studied PXT3003 dosages on the following endpoints: 
 ▪ Arm and leg sub-items of ONLS; ▪ Charcot-Marie-Tooth Neuropathy Score version 2 (CMTNS-v2), including its sub-items; ▪ Nine-hole Peg Test (9-HPT) performed on non-dominant hand; ▪ Quantified Muscular Testing (QMT) by Hand grip and Foot dorsiflexion dynamometry (mean of both sides); ▪ Time to walk 10 meters; ▪ Electrophysiological parameters assessing sensory and motor responses of ulnar and radial nerves (non-dominant side) including: 
 ○ Compound Muscle Action Potential (CMAP) on ulnar nerve; ○ Sensory Nerve Action Potential (SNAP) on radial nerve; ○ Nerve conduction velocity (NCV); ▪ Quality of life measured by: 
 ○ EuroQol 5-Dimensional Health-related Quality of Life scale (EQ-5D); ○ VAS on self-assessment of the individualized main impairment in daily activities defined at baseline with the patient.
Secondary safety endpoints	
Safety and tolerability of PXT3003 will be compared to placebo on the following parameters:
 
 - Incidence of all Treatment Emergent Adverse Events (TEAEs); they will be evaluated by type/nature, severity/intensity, seriousness, duration, relationship to study drug, and outcome; - Incidence of related TEAEs (including possibly and probably related TEAEs) with a moderate or severe intensity; - Incidence of AE leading to withdrawal of study drug; - Incidence of Serious Adverse Events (SAEs); - Change in physical examination, vital signs (blood pressure and heart rate), 12-lead ECG, and laboratory data (hematology and blood chemistry).

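### Sections 12.1.1.3 and 12.1.1.4 classify a multi-day admission to investigate an adverse event in opposite ways, so such events can drop out of the SAE count and the 24-hour notification duty

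*Combined protocol and SAP*

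**What the plan says.** Section 12.1.1.3 lists the criteria that make an untoward event serious. One is that it "requires patient's hospitalization or prolongation of existing hospitalization". A footnote defines hospitalisation by length alone: inpatient care extending beyond a single calendar day. Neither the criterion nor the footnote makes an exception for the reason for the stay.

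The next section is headed "12.1.1.4 SAE waived from expedited regulatory reporting to regulatory authorities". A reader of that heading expects events that remain SAEs but need no expedited report. The text below it goes further: "the following events will not be designated as a serious adverse event (SAE"). Four kinds of admission follow. Three are planned care for the indication, stays arranged before inclusion, and overnight stays for social or travel reasons. The fourth is "admission for diagnostic evaluation of an AE".

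SAE incidence is a safety endpoint compared with placebo (synopsis and section 8.4.2). Section 14.6 summarises it by treatment group with 95% confidence intervals, and gives 95% intervals for differences between groups. Section 12.1.3 attaches the 24-hour notification duty to SAEs. Section 12.1.2 requires every adverse event to be recorded in the CRF, serious or not.

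**The concern.** The three other listed admissions are not prompted by a new untoward event, so excluding them from the SAE category does little harm. The planned-care item even carries its own safeguard: it applies only to admissions "not associated with any deterioration in condition". The diagnostic item is different in kind. It exists only because an adverse event has occurred, and it sets no limit on length of stay, on deterioration or on outcome.

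Two things are at stake. The SAE table can omit events that the protocol's own definition would include. Notification to the sponsor's pharmacovigilance representatives can also fail to be triggered for an event that 12.1.1.3 calls serious. In addition, a site that follows 12.1.1.3 and a site that follows 12.1.1.4 will classify the same event differently, so the endpoint would not have one definition across the trial.

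**Working it through.** The plan states no figure on this point, so there is none to reproduce. The check is a comparison of the texts, followed by an illustration of size.

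**Step 1. One case under both sections.** A patient has an unexplained adverse event and is admitted for three days of work-up. No other seriousness criterion is met.

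| Question | 12.1.1.3 | 12.1.1.4 |
|---|---|---|
| Inpatient stay beyond one calendar day? | Yes, so hospitalisation | Length not considered |
| Does the purpose of the stay matter? | No | Yes, diagnostic evaluation |
| Classification | SAE | Not an SAE |

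**Step 2. Where the conflict arises.** Stays within one calendar day are not hospitalisation under the footnote, so the two sections agree on them. An event that also meets another criterion, such as being medically important, can still be called serious. The conflict is confined to stays beyond one calendar day for events with no other ground for seriousness.

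**Step 3. Does another section settle it?** The heading of 12.1.1.4 suggests that only expedited reporting was meant to be waived, but the operative sentence removes SAE status. Sections 8.4.2, 12.1.2, 12.1.3 and 14.6 do not bring the listed events back into the SAE count or under the 24-hour duty.

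**Step 4. Direction.** 12.1.1.4 only takes events away. Applying it can leave the SAE count equal to or below the count under 12.1.1.3, never above it.

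**Step 5. Size, illustration only.** Let p be the proportion of patients with an SAE under 12.1.1.3, and s the share of those who qualify only through a diagnostic admission. The documents give neither, so p from 3% to 10% and s from 10% to 30% are assumptions. The patient numbers, 100 per arm and 300 in total, are from section 14.3.

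- Reported proportion = p × (1 − s)
- Expected patients lost per 100 = 100 × p × s
- Chance of at least one lost in 300 = 1 − (1 − p × s)^300

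| p | s | Reported | Lost per 100 | At least one lost in 300 |
|---|---|---|---|---|
| 3% | 10% | 2.7% | 0.3 | 59% |
| 3% | 30% | 2.1% | 0.9 | 93% |
| 6% | 10% | 5.4% | 0.6 | 84% |
| 6% | 30% | 4.2% | 1.8 | over 99% |
| 10% | 10% | 9.0% | 1.0 | 95% |
| 10% | 30% | 7.0% | 3.0 | nearly 100% |

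**Step 6. Comparison between arms.** If s is the same in every arm, the factor (1 − s) cancels from the risk ratio, which is unchanged. The risk difference shrinks by that factor. For assumed true rates of 10% and 5%, the difference of 5.0 points becomes 5.0 × 0.9 = 4.5 points at s = 10%, or 5.0 × 0.7 = 3.5 points at s = 30%.

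**The case against.** The strongest reply is that 12.1.1.3 is the general rule and 12.1.1.4 a study-specific list of exceptions, so the two form one rule. That would be convincing if the heading of 12.1.1.4 announced exceptions to the SAE definition. It announces a reporting waiver, so the section disagrees with itself and leaves the exception in doubt.

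A second reply is that the item exempts the admission and not the event behind it. Section 12.1.1.1 draws that line for surgery: the procedure is not an adverse event, but the underlying condition may be. The reading is possible, but 12.1.1.4 does not state it. Even on that reading, the event loses the one criterion it met if hospitalisation was the only ground for seriousness.

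Several limits do stand. A reader might infer that these events vanish from the safety data. They do not: section 12.1.2 keeps each one in the CRF with severity, relationship, outcome and information on seriousness. Those that are treatment-emergent count in TEAE incidence, and the monitoring board's remit in section 14.7 is safety data as a whole. A reader might also infer that the comparison with placebo is biased in favour of the drug. The documents give no support for that, since the rule is the same in every arm and the treatment is double-blind. Nor is there much force in the thought that the board will go on seeing too few events for the untested higher dose. That arm has been discontinued, so what matters is how its existing events are classified. Finally, section 12.1.3 refers to SAE form instructions and a Safety Management Plan, which may clarify the point. They are not part of these documents, and the protocol should be clear without them.

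**Conclusion.** The conflict is real and lies in the wording. An event that leads to a diagnostic admission beyond one calendar day, and meets no other seriousness criterion, is an SAE under 12.1.1.3 and not under 12.1.1.4. If sites follow 12.1.1.4, SAE incidence can only be reduced and 24-hour notification is not required. If sites differ, the endpoint is defined inconsistently.

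A reader might go further and say that SAEs will be under-counted, or name a number. The documents support only that they can be. An actual loss requires that such admissions occur, that no other criterion applies to them, and that sites follow 12.1.1.4 as written. Under the assumed ranges the loss is 0.3 to 3 patients per 100, but neither range has an anchor in the documents. For the dose 2 arm, which was stopped early, full-duration rates would probably overstate the loss. The point deserves correction because it concerns the definition of a stated safety endpoint, not because a large effect has been shown.

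**What to change.** Reconcile 12.1.1.3 and 12.1.1.4 in one of two ways:

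- remove the diagnostic-evaluation item from the list in 12.1.1.4; or
- limit 12.1.1.4 to what its heading says, a waiver from expedited reporting, and state that events with a diagnostic admission are still recorded as SAEs and counted in the section 14.6 summary.

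Then check all recorded adverse events with a hospital admission against 12.1.1.3 before database lock, in all arms including dose 2. The check matters more than the new wording. The current version dates from December 2017, and the last patient out is expected in Q1 2018 (Q3 2018 in Germany), so most events will already have been classified.

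The cost is a wording change, a few more SAE forms and possibly a slightly higher reported SAE rate. The items that section 12.1.2 requires for each adverse event do not name hospital admission, so the check may need site source documents for events recorded as non-serious.
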